### *Classification of Causality*

The relationship of each AE to the study drug will be recorded on the CRF in response to the following question:

Is there a reasonable possibility that the study drug caused the AE?

Yes (related)      A causal relationship between the study drug and the AE is a reasonable possibility.

No (not related)    A causal relationship between the study drug and the AE is not a reasonable possibility.

### **8.5.1.4.2 SERIOUS ADVERSE EVENTS AND EVENTS ASSOCIATED WITH SPECIAL SITUATIONS**

An SAE is any untoward medical occurrence that at any dose:

- Results in death
- Is life-threatening (ie, the subject was at immediate risk of death from the adverse event as it occurred; this does not include an event that, had it occurred in a more severe form or was allowed to continue, might have caused death)
- Requires inpatient hospitalization or prolongation of existing hospitalization
- Results in persistent or significant disability/incapacity

- Is a congenital anomaly/birth defect (in the child of a subject who was exposed to the study drug)

Other important medical events that may not be immediately life-threatening or result in death or hospitalization but, when based on appropriate medical judgment, may jeopardize the subject or may require intervention to prevent one of the outcomes in the definition of SAE listed above should also be considered SAEs. Medical and scientific judgment should be exercised in deciding whether expedited reporting is appropriate in such situations.

In addition to the above, events associated with special situations include pregnancy or exposure to study drug through breastfeeding; AEs associated with study drug overdose, misuse, abuse, or medication error. These events associated with special situations are to be captured using the SAE procedures but are to be considered as SAEs only if they meet one of the above criteria. All AEs associated with special situations are to be reported on the CRF whether or not they meet the criteria for SAEs.

All SAEs must be followed to resolution or, if resolution is unlikely, to stabilization.

The following hospitalizations are not considered to be SAEs because there is no “adverse event” (ie, there is no untoward medical occurrence) associated with the hospitalization:

- Hospitalizations for respite care
- Planned hospitalizations required by the protocol
- Hospitalization planned before informed consent (where the condition requiring the hospitalization has not changed after study drug administration)
- Hospitalization for administration of study drug or insertion of access for administration of study drug
- Hospitalization for routine maintenance of a device (eg, battery replacement) that was in place before study entry

#### 8.5.1.4.3 LABORATORY MEASUREMENTS

Clinical laboratory tests to be performed, including hematology, chemistry, and urinalysis, are summarized in [Table 4](#). Subjects should be in a seated or supine position during blood collection. The Schedule of Procedures/Assessments ([Table 5](#) and [Table 6](#)) shows the visits and time points at which blood for clinical laboratory tests and urine for urinalysis will be collected in the study.

**Table 4 Clinical Laboratory Tests**

Category	Parameters
Hematology	Hematocrit, hemoglobin, platelets, RBC count, and WBC count with differential (bands, basophils, eosinophils, lymphocytes, monocytes, neutrophils)
Chemistry	
Electrolytes	Bicarbonate, chloride, potassium, sodium, calcium, magnesium, phosphorus
Liver function tests	ALT, alkaline phosphatase, AST, conjugated (direct) bilirubin a , total bilirubin, INR b
Renal function tests	BUN or urea, creatinine
Other chemistries	Albumin, amylase, glucose, LDH, lipase, total protein
Thyroid function tests c	Thyroid stimulating hormone, free T4 level
Urinalysis for microscopy d	RBCs
Urine dipstick testing d,e	Blood, protein, glucose
Other	Pregnancy test (serum or urine $\beta$ -hCG)

ALT = alanine aminotransferase, AST = aspartate aminotransferase, BUN = blood urea nitrogen,  $\beta$  hCG = beta-human chorionic gonadotropin, INR = International Normalized ratio, LDH = lactate dehydrogenase, RBC = red blood cells, T4 = thyroxine, TSH = thyroid stimulating hormone, WBC = white blood cells.

- a. Direct bilirubin should be assessed if total bilirubin is elevated.
- b. INR should only be performed as part of the screening assessment. During the study, INR should be performed if clinically indicated.
- c. Thyroid function will be assessed every 2 cycles for all subjects.
- d. If urine dipstick testing suggests a urinary tract infection, or if clinically indicated, a urine microscopy, culture, and sensitivity should be performed at the institution's laboratory
- e. If urine protein is  $\geq 2+$ , then a spot test for protein-creatinine ratio and if possible, a 24-hour urine collection should be done to quantify the 24 hour urine protein excretion.

All clinical laboratory tests during the study will be performed at qualified local laboratories. All hematology, blood chemistry (including pregnancy test, as applicable), and urinalysis samples are to be obtained prior to study drug administration and sent to the local laboratory on the day of collection unless otherwise instructed.

Clinical chemistry and hematology results must be reviewed prior to administration of study drug on Cycle 1 Day 1 and within 48 hours after dispensing study drug for all subsequent cycles. Scheduled assessments may be performed within 72 hours prior to the visit. If  $\geq$  Grade 3 hematologic or clinical chemistry toxicity, repeat laboratory test and AEs assessment at least every 3 days (until improvement to  $<$  Grade 3). Refer to [Table 1](#) (study drug dose reduction and interruption instructions) for the management of clinically significant laboratory abnormalities. Every effort should be made to collect samples for analysis at the local laboratory at the same time.

A laboratory abnormality may meet the criteria to qualify as an AE as described in this protocol (see [Section 8.5.1.4.1](#) and the CRF Completion Guidelines. In these instances, the

AE corresponding to the laboratory abnormality will be recorded on the Adverse Event CRF (see [Section 8.5.4.3.2](#)).

#### 8.5.1.4.4 VITAL SIGNS AND WEIGHT MEASUREMENTS

Vital sign measurements (ie, systolic and diastolic blood pressure [BP] [mmHg], pulse [beats per minute], respiratory rate [per minute]), body temperature (in centigrade), weight (kg), and height (cm) will be obtained at the visits designated in the Schedule of Assessments ([Table 5](#) and [Table 6](#)) by a validated method. Blood pressure and pulse will be measured after the subject has been resting for 5 minutes. All BP measurements should be performed on the same arm, preferably by the same person. On Cycle 1 Day 8, subjects will be contacted by telephone to assess for the development of early toxicity. Subjects will be provided with a BP cuff to monitor BP at home or can have the measurement done by a local healthcare provider, and will report the C1D8 measurement at telephone contact. An unscheduled visit can occur prior to C1D15 if deemed necessary by the investigator.

Only 1 BP measurement is needed for subjects with systolic BP <95th percentile (BP <140 mm Hg) and diastolic BP <95th percentile (BP <90 mmHg). If the subject's initial BP measurement is elevated (systolic BP  $\geq$ 95th percentile [ $\geq$ 140 mmHg] or diastolic BP  $\geq$ 95th percentile [ $\geq$ 90 mmHg]), the BP measurement should be repeated at least 5 minutes later. The mean value of 2 measurements at least 5 minutes apart is defined as 1 BP assessment. If the BP assessment (ie, the mean of the 2 BP measurements obtained at least 5 minutes apart) is elevated (systolic BP  $\geq$ 95th percentile [ $\geq$ 140 mm Hg] or diastolic BP  $\geq$ 95th percentile [ $\geq$ 90 mm Hg]), a confirmatory assessment should be obtained at least 30 minutes later by performing 2 measurements (at least 5 minutes apart) to yield a mean value.

#### 8.5.1.4.5 PHYSICAL EXAMINATIONS

Physical examinations will be performed as designated in the Schedule of Procedures/Assessments ([Table 5](#) and [Table 6](#)). Documentation of the physical examination will be included in the source documentation at the site. Only changes from screening physical examination findings that meet the definition of an AE will be recorded on the Adverse Events CRF.

#### 8.5.1.4.6 ELECTROCARDIOGRAMS

Electrocardiograms will be obtained as designated in the Schedule of Assessments ([Table 5](#) and [Table 6](#)). Complete, standardized, 12-lead ECG recordings that permit all 12 leads to be displayed on a single page with an accompanying lead II rhythm strip below the customary 3 $\times$ 4 lead format are to be used. In addition to a rhythm strip, a minimum of 3 full complexes should be recorded from each lead simultaneously. If possible, subjects must be in the recumbent position for a period of 5 minutes prior to the ECG.

An ECG abnormality may meet the criteria of an AE as described in this protocol (see [Section 8.5.1.4.1](#)) and the CRF Completion Guidelines. In these instances, the AE corresponding to the ECG abnormality will be recorded on the Adverse Events CRF.

For ECG abnormalities meeting criteria of an SAE (see Serious Adverse Events and Other Events of Interest), the study site must fax the SAE report including the ECG report to the number indicated in the Investigator File using the SAE reporting form (see [Section 8.5.4.1](#)).

#### 8.5.1.4.7 OTHER SAFETY ASSESSMENTS

##### **Pregnancy Test**

A serum  $\beta$ -hCG test will be performed for females of childbearing potential (see definition included in the Inclusion/Exclusion criteria, [Sections 8.3.1](#) and [8.3.2](#)). A serum or urine pregnancy test will be performed at Screening, Baseline (or within 72 hours prior to the first dose of study medication), on Day 1 of each cycle from Cycle 2 onwards, and at the Off-treatment Visit in women of childbearing potential. Blood and urine samples will be taken at designated time points as specified in the Schedule of Assessments ([Table 5](#) and [Table 6](#)).

##### **Echocardiogram**

An echocardiogram to assess LVEF will be performed during the screening phase, every 16 weeks following the first dose of study drug while the subject is on treatment or sooner, if clinically indicated, and at (or within 1 week following) the off-treatment assessment. LVEFs as assessed by the institution will be entered onto the CRF. Investigator assessment will be based upon institutional reports.

#### 8.5.1.5 Other Assessments

Health-related quality of life (HRQoL) assessment will be performed per the Schedule of Assessments ([Table 5](#) and [Table 6](#)). Impact of treatment on HRQoL will be assessed using the PedsQL (including the Generic Core Scales and Cancer Module). Data will be collected as parent-report for toddlers (2 to 4 years) and as self-report for subjects aged  $\geq 5$  years. Self-report is the preferred data collection for all subjects aged  $\geq 5$ , however to improve adherence of participation, it is also acceptable to collect the data as proxy report by observers including parents and caregivers.

The PedsQL is a modular instrument designed to measure HRQoL in pediatric and adults population. The PedsQL 4.0 Generic Core Scales are multidimensional child self-report and parent proxy-report scales developed as the generic core measure to be integrated with the PedsQL disease specific modules. The PedsQL 3.0 Cancer Module was designed to measure pediatric cancer specific HRQOL.

It is best practice and strongly recommended that the PedsQL measurement modules are administered to randomized subjects prior to drug administration or any other interaction with site staff.

## 8.5.2 Schedule of Procedures/Assessments

### 8.5.2.1 Schedule of Procedures/Assessments

**Table 5** presents the schedule of procedures/assessments for the Randomization Phase of the study.

**Table 6** presents the schedule of procedures/assessments for the Extension Phase of the study.

**Table 5 Schedule of Assessments in Study E7080-G000-230 – Randomization Phase**

Phase	Prerandomization		Randomization a (All cycles are 21 days in duration)																		
	Screening b	Baseline c	Treatment d																Off-Tx	Follow-up e	
Period	1	2	3	4	5	6	7	8	9	10	11	12	13	14	15	16	17	18+			
Visit	1	2	3	4	5	6	7	8	9	10	11	12	13	14	15	16	17	18+			
Cycle			Cycle 1			Cycle 2			Cycle 3			Cycle 4			Cycle 5			Cycle 6-X			
Day	-28 to -2	-1	1	8	15	1	8	15	1	8	15	1	8	15	1	8	15	1			
Procedures/Assessments																					
Informed consent	X																				
Inclusion/exclusion	X	X																			
Randomization (IVRS)			X																		
Demographic data	X																				
Medical/surgical history	X	X																			
Prior medication/ procedures	X	X																			
Pregnancy test f	X	X				X			X			X			X			X	X	X	X
Lansky play score/ Karnofsky PS g	X	X	X			X			X			X			X			X		X	
TNM Staging	X																				
Physical examination h	X	X	X		X	X		X	X			X			X			X	X	X	X
Vital signs i	X	X	X	X j	X	X		X	X			X			X			X	X	X	X
12-lead ECG k	X		X			X												X	X		
Echocardiogram l	X	Performed every 16±2 weeks following the first dose of study drug or sooner, if clinically indicated																X			
Clinical chemistry and hematology m	X	X			X	X		X	X			X			X			X	X	X	X
Urine dipstick testing n	X	X			X	X		X	X			X			X			X	X	X	X
PK blood samples o			X		X	X															
Study treatment p			Arm A: Combination of lenvatinib (QD) + ifosfamide + etoposide (Days 1-3 of Cycles 1-5 only) [based on BSA calculations at Day 1 of each Cycle]; after Cycle 5 subjects will receive lenvatinib alone. Arm B: Ifosfamide + etoposide (Days 1-3 of Cycles 1-5 only) [based on BSA calculations at Day 1 of each Cycle]																		

**Table 5 Schedule of Assessments in Study E7080-G000-230 – Randomization Phase**

Phase	Prerandomization		Randomization a (All cycles are 21 days in duration)																		
	Screening b	Baseline c	Treatment d															Off-Tx	Follow-up e		
Period	1	2	3	4	5	6	7	8	9	10	11	12	13	14	15	16	17	18+			
Visit	1	2	3	4	5	6	7	8	9	10	11	12	13	14	15	16	17	18+			
Cycle			Cycle 1			Cycle 2			Cycle 3			Cycle 4			Cycle 5			Cycle 6-X			
Day	-28 to -2	-1	1	8	15	1	8	15	1	8	15	1	8	15	1	8	15	1			
Procedures/Assessments																					
Palatability Questionnaire g			X																		
Tumor assessments: CT/MRI f	X		CT chest and CT/MRI of other areas of known disease at Screening plus any areas of newly suspected disease should be performed every 6±1 week or sooner if clinically indicated until Week 18±1 week, then every 9±1 weeks until Week 54±1 week. Thereafter, to be performed every 12±2 weeks until documentation of PD.															X			
Brain CT/MRI f	X		Brain scans will be performed at screening as clinically indicated, and thereafter during treatment if clinically indicated. For subjects with protocol-eligible, treated brain metastases at Screening, brain scans should be performed at all tumor assessment time points.																		
Height t		X	X												X				X	X	X
Tanner Stage u		X																	X	X	X
Proximal Tibial growth plates x-ray t		X																X			
HRQoL		X	HRQoL will be collected on C2D1, C3D1, Week 18, C8D1, and C18D1															X			
Pharmacodynamic biomarkers v		X		X	X										X				X		
Archival tumor block or slides w			X																		
Survival x						X															X
Concomitant medications y			Throughout															X			
AEs/SAEs z			Throughout															X			

AE = adverse event, BP = blood pressure, C1D1 = Cycle 1 Day 1, C1D2 = Cycle 1 Day 2, C1D8 = Cycle 1/Day 8, C1D15 = Cycle 1 Day 15, CR = complete response, CT = computerized tomography, h = hour, HR = heart rate, HRQoL = Health-Related Quality of Life, IV = intravenous, IVRS = Interactive Voice Response System, MRI = magnetic resonance imaging, PD = progressive disease/disease progression, PK = pharmacokinetics, PR = partial response, PS =

**Table 5 Schedule of Assessments in Study E7080-G000-230 – Randomization Phase**

Phase	Prerandomization		Randomization a (All cycles are 21 days in duration)																	
	Screening b	Baseline c	Treatment d																Off-Tx	Follow-up e
Period	1	2	3	4	5	6	7	8	9	10	11	12	13	14	15	16	17	18+		
Visit	1	2	3	4	5	6	7	8	9	10	11	12	13	14	15	16	17	18+		
Cycle			Cycle 1			Cycle 2			Cycle 3			Cycle 4			Cycle 5			Cycle 6-X		
Day	-28 to -2	-1	1	8	15	1	8	15	1	8	15	1	8	15	1	8	15	1		
Procedures/Assessments																				

performance score, RECIST 1.1 = Response Evaluation Criteria in Solid Tumors, version 1.1, RR = respiratory rate, SAE = serious adverse event, TNM = tumor-node-metastasis, Tx = treatment.

- a. During Cycle 1, efforts should be made to conduct study visits on the day scheduled ( $\pm 1$  day); from Cycle 2 onwards, efforts should be made to conduct study visits on the day scheduled ( $\pm 3$  days).
- b. The results of all screening assessments and evaluations must be completed and reviewed by the investigator prior to the Baseline Visit. Informed consent may be obtained up to 4 weeks prior to C1D1.
- c. Baseline assessments can be performed on Day -1 or on C1D1 prior to treatment.
- d. For subjects randomized to Arm A, subjects benefiting from study treatment in the opinion of the investigator will continue lenvatinib treatment until PD, intolerable toxicity, noncompliance with safety or efficacy assessments, voluntary discontinuation by the subject at any time, or study termination by the sponsor, whichever occurs first.
- e. Subjects will be followed every 12 weeks until documentation of PD or until death as per the protocol.
- f. A serum or urine pregnancy test will be performed at the Screening and Baseline Visits (or within 72 hours prior to the first dose of study medication), on Day 1 of each cycle from Cycle 2 onwards, if pregnancy is suspected, and at the Off-treatment Visit in women of childbearing potential.
- g. A Lansky play score or Karnofsky performance status score will be obtained at the Screening, Baseline, and C1D1 Visit, and Day 1 of every subsequent cycle visit thereafter.
- h. A comprehensive physical examination (including a neurological examination) will be performed at the Screening and Baseline Visits (only if screening physical examination was performed  $>7$  days prior to C1D1), C1D15, C2D1, C2D15, and Day 1 visit of each subsequent cycle, and at the Off-treatment Visit. A symptom-directed physical examination will be performed on C1D1 and at any time during the study, as clinically indicated.
- i. Assessments will include vital signs (resting BP, HR, RR, and body temperature) and weight. Blood pressure that is consistently above the 95th percentile for sex, age, and height/length requires further evaluation. Refer to hypertension management guidelines in [Section 8.4.1.1.2](#).
- j. On Cycle 1 Day 8, subjects will be contacted by telephone to assess for the development of early toxicity. Subjects will be provided with a BP cuff to monitor BP at home or can have the measurement done by a local healthcare provider, and will report the C1D8 measurement at telephone contact. An unscheduled visit can occur prior to C1D15 if deemed necessary by the investigator.
- k. Single 12-lead ECG. If possible, subjects must be in the recumbent position for a period of 5 minutes prior to the ECG. ECG should be conducted at

- p. Subjects randomized to Arm A will continue to receive lenvatinib only after completion of 5 cycles with lenvatinib+ifosfamide+etoposide until progressive disease, unacceptable toxicity, subject request, study termination by the sponsor, subject noncompliance with safety or efficacy assessments, or withdrawal of consent. Subjects randomized to Arm B will be off-treatment after 5 cycles of ifosfamide+etoposide.
- q. All subjects who receive suspension formulation, with the exception of subjects using a nasogastric or gastrostomy tube, must complete the Palatability Questionnaire according to the Schedule of Assessments. If the subject is unable to complete the questionnaire this must be done by their parents or their legal guardian.
- r. **Screening:** Tumor assessments of the chest, abdomen, pelvis, and other areas of known disease or newly suspected disease should be performed within 28 days prior to C1D1. Scans of the abdomen, pelvis, and other areas of the body may be done with MRI instead of CT, but evaluation of the chest should be done with CT. CT scans should be performed with oral and iodinated IV contrast and MRI scans should be performed with IV gadolinium chelate.

**Table 5 Schedule of Assessments in Study E7080-G000-230 – Randomization Phase**

Phase	Prerandomization		Randomization a (All cycles are 21 days in duration)																	
	Screening b	Baseline c	Treatment d																Off-Tx	Follow-up e
Period	1	2	3	4	5	6	7	8	9	10	11	12	13	14	15	16	17	18+		
Visit	1	2	3	4	5	6	7	8	9	10	11	12	13	14	15	16	17	18+		
Cycle			Cycle 1			Cycle 2			Cycle 3			Cycle 4			Cycle 5			Cycle 6-X		
Day	-28 to -2	-1	1	8	15	1	8	15	1	8	15	1	8	15	1	8	15	1		
Procedures/Assessments																				

**Treatment Phase:** Tumor assessments of the chest, and other areas of known disease at Screening or newly suspected disease should be performed every  $6\pm 1$  weeks from C1D1 until Week  $18\pm 1$  week, then every  $9\pm 1$  weeks until Week  $54\pm 1$  week, and thereafter, every  $12\pm 2$  weeks until documentation of PD during the Treatment Phase (or sooner if there is evidence of progressive disease) and should utilize the same methodology (CT or MRI) and scan acquisition techniques (including use or nonuse of IV contrast) as was used for the screening assessments. Tumor response will be assessed according to RECIST 1.1. Subjects who discontinue must complete the off-treatment tumor assessment. Any CR or PR must be confirmed not less than 4 weeks following the initial achievement of the response. After treatment discontinuation, tumor assessment should continue to be performed according to the schedule: every  $6\pm 1$  weeks until Week  $18\pm 1$  week, then every  $9\pm 1$  weeks until Week  $54\pm 1$  week, thereafter, to be performed every  $12\pm 2$  weeks until documentation of progression or start of a new anticancer agent.

- s. Brain CT with contrast or MRI pre- and post- gadolinium contrast will be performed at the Screening Visit as clinically indicated, and thereafter during treatment as clinically indicated. For subjects with protocol-eligible treated brain metastases, brain CT/MRI will be performed at all tumor assessment time points.
- t. Height will be assessed at the Baseline Visit, Day 1 of every 4 cycles during the Treatment Phase, at the Off-treatment Visit and every 3 months during the Post-treatment Follow-up. Proximal tibial growth plates x-rays should be conducted at baseline and at the Off-treatment Visit. If the growth plates are closed at baseline then the subject does not need a reassessment at the Off-treatment Visit. Tibial growth plate x-rays will be optional for Germany.
- u. Tanner Stage will be assessed at the Baseline Visit, at the Off-treatment Visit, and annually thereafter during the Post-treatment Follow-up.
- v. Blood samples will be collected only from subjects in Arm A at the Baseline Visit, C1D15, Day 1 of Cycles 2, 4, and 6, for assessment for blood serum sample to measure factors implicated in angiogenesis.
- w. An archival tumor sample from the most recent surgery or biopsy for identification of predictive biomarkers and pathology review may be collected from subjects in Arm A at any time during the study, unless no such material is available.
- x. Survival data will be collected every 3 months until death as per the protocol. All anticancer therapies will be collected.
- y. Concomitant medications will be recorded throughout the study and for 30 days after last dose. All anticancer therapy will be recorded until time of death or termination of Survival Follow-up.
- z. AEs will be recorded from the date of signed informed consent, throughout the study, and for 30 days after last dose. SAEs irrespective of relationship to study treatment must be reported as soon as possible but not later than 24 hours.

**Table 6** presents the Schedule of Procedures/Assessments for the Extension Phase of the study.

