### 8.7.1.1 Study Endpoints

#### 8.7.1.1.1 PRIMARY ENDPOINT

- Progression-free survival rate at 4 months (PFS-4m rate) by IIR is defined as the percentage of subjects who are alive and without PD at 4 months from the randomization date as determined by IIR of radiological imaging using RECIST 1.1. The PFS-4m rate is estimated on the full analysis set for this study using the K-M method.

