#### 8.1.2.1 Treatment Period

The Treatment Period for each subject will begin at the time of randomization and will end at the completion of the Off-Treatment Visit which will occur within 30 days after the final dose of study treatment.

Subjects will receive study treatment as continuous 21-day cycles in both treatment arms. Treatment cycles will be counted continuously regardless of dose interruptions. If chemotherapy administration is precluded on Day 1 of a treatment cycle, the subject may resume treatment once recovered at the discretion of investigator. Subsequent chemotherapy will be administered every 21 ( $\pm 1$ ) days starting from the timepoint it was resumed. Subjects will undergo safety and efficacy assessments as defined in the Schedule of Procedures/Assessments ([Table 5](#)). Subjects randomized to Arm A will continue to receive lenvatinib until disease progression (PD) confirmed by IIR, development of unacceptable toxicity, subject request, withdrawal of consent, or study termination by the sponsor, whichever occurs first.

Disease progression (PD) must be confirmed by IIR prior to the investigator discontinuing study treatment for a subject. In situations where the investigator judges that alternative treatments must be instituted immediately for a subject's safety, study drugs may be discontinued without waiting for IIR confirmation of radiographic evidence of PD. If possible, before discontinuation of the subject from the study, the investigator should consult with the sponsor.

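### The off-treatment tumor scan gives Arm B completers an assessment shortly before the 4-month landmark that Arm A subjects still on lenvatinib do not have, which biases PFS-4m toward lenvatinib

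*Protocol*

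**What the plan says.** The primary endpoint is the Kaplan-Meier proportion "alive and without PD at 4 months from the randomization date" by independent imaging review (Protocol 8.7.1.1.1). PFS is dated to the first documentation of progression or death (8.7.1.1.2).

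Scheduled scans run from Cycle 1 Day 1 in both arms: every 6 ±1 weeks to Week 18, every 9 weeks to Week 54, then every 12 weeks (8.5.1.2.1 and Table 5).

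The CT/MRI row of Table 5 also ends in a mark after the calendar text. The footnote to that row (r in one copy of the protocol text, q in the other) says "Subjects who discontinue must complete the off-treatment tumor assessment". It then says that scanning continues on the calendar after discontinuation, so the off-treatment scan is an addition and not a replacement.

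The arms leave treatment at different times. Chemotherapy in Arm B is "ifosfamide + etoposide (Days 1-3 of Cycles 1-5 only", with 21-day cycles, and the study-treatment footnote states "Subjects randomized to Arm B will be off-treatment after 5 cycles of ifosfamide+etoposide". For Arm A, "after Cycle 5 subjects will receive lenvatinib alone". Section 8.1.2.1 ends each subject's Treatment Period at the "Off-Treatment Visit which will occur within 30 days after the final dose of study treatment".

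**The concern.** The number of scans before the landmark depends on the arm, because one scan is tied to leaving treatment and the two arms leave treatment on different timetables. PFS takes the date of the scan that shows progression, so an additional scan in one arm moves that arm's events earlier even if the disease behaves identically.

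At stake is the primary comparison of an open-label superiority trial tested at one-sided 0.1. Section 8.2 relies on blinded central review to avoid bias, but central review can read only the scans that were taken. The same asymmetry moves Arm B dates earlier in the PFS hazard ratio and median.

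**Working it through.** **Calendar.** Inputs are from Table 5 and 8.1.2.1. Randomization is taken to fall on Cycle 1 Day 1, where Table 5 places it, and 4 months is taken as 365.25/3 days because the protocol gives no day count.

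- Last Arm B dose without delay: Cycle 5 Day 3 = 4 × 21 + 3 = Day 87.
- Off-Treatment Visit: Day 87 to Day 87 + 30 = Day 117 (Weeks 12.4 to 16.7).
- Week 18 ±1 window: 17 × 7 = Day 119 to 19 × 7 = Day 133.
- Landmark: 365.25/3 = Day 121.75 (Week 17.4).

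The off-treatment window closes before both the Week 18 window and the landmark, so without delay the Week 18 scan cannot double as the off-treatment scan. If scan dates are uniform in the Week 18 window, only (121.75 − 119)/14 = 20% of Week 18 scans precede the landmark. For most Arm A subjects still on lenvatinib, the last scan that counts is Week 12.

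**Approximate size by hand.** With exponential progression and a true PFS-4m of 25%, S(w) = 0.25^(w/17.39), with w in weeks. If Arm A is last scanned at Week 12, its observed rate is S(12) = 38.4%. If Arm B is last scanned at the middle of its off-treatment window (Day 102, Week 14.57), its rate is S(14.57) = 31.3%. The difference is 7.1 points with no true effect.

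**Simulation.** Settings: 36 per arm, the same true rate in both arms, exponential progression, scan dates uniform within their windows, no deaths or censoring, and the protocol's 80% CI rule with a binomial standard error. The plan's own figure, a one-sided error of 10%, is reproduced at 9.4% when both arms share one schedule, with a difference of 0.0 points. With a true rate of 25% in both arms:

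| Scenario | Arm A | Arm B | Spurious gain | One-sided error |
|---|---|---|---|---|
| No off-treatment scan in either arm | 35.9% | 35.9% | 0.0 points | 9.4% |
| Arm B scan uniform on Days 87-117 | 35.9% | 30.2% | 5.7 points | 22% |
| Arm B scan on Days 87-91 | 35.9% | 34.0% | 1.9 points | 12.5-13% |
| Arm B scan on days 28-30 after last dose | 35.9% | 26.7% | 9 points | 33-34% |
| Only half of Arm B scanned | 35.9% | 33.1% | 2.8 points | 15% |
| 25.8% of Arm A also scanned | 34.5% | 30.3% | 4.2 points | 18-19% |
| Off-treatment scan 3 weeks later (chemotherapy delay) | 35.9% | 31.6% | 4.3 points | 18% |

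The 25.8% is the rate of discontinuation for adverse events reported for this combination in Study 207 (6.3.1).

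With a true rate of 40% in both arms, the gain is 5 to 9 points and the error about 20 to 30%. With 55%, it is 4 to 8 points and about 17 to 27%.

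**Dependence on the landmark.** Repeating the Days 87-117 case with a later landmark gives 3.6 points and 17.5% at Day 126, and 0.1 points and about 10% at Day 133, the end of the Week 18 window.

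**The case against.** **The footnote may mean early stoppers only.** Arm B completers are called off-treatment rather than discontinued. Section 8.1.2.2 ties continued scanning to early discontinuation, and 8.5.1.2.1 treats Week 18 as the end of the chemotherapy period. The table is also broken in the available text, so the column of the trailing mark cannot be read directly. This leaves some doubt but is the less likely reading. Every subject's Treatment Period ends at an Off-Treatment Visit. The echocardiogram, HRQoL and tibial x-ray rows, all described elsewhere as done at that visit, carry the same single trailing mark.

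**The effect may be diluted.** A visit by Day 91 can coincide with the Week 12 ±1 scan and then adds nothing. Arm A subjects who stop early are scanned too, chemotherapy may slip, and clinically indicated scans are allowed in both arms. Deaths, which are not modelled, would reduce the effect further. All of this stands and lowers the size. None of the cases tested reverses the direction.

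**The landmark may be the real problem.** A reader might infer that the off-treatment scan distorts PFS-4m wherever the landmark sits. The documents do not support that: the PFS-4m bias disappears if the landmark covers the whole Week 18 window. The earlier dating of Arm B events in the PFS curve would remain; its size was not calculated.

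**Two other inferences go too far.** One is that all progression between Weeks 12 and 16 counts against Arm B and none against Arm A. In Arm B only progression present by the actual scan date is caught, and in Arm A an early Week 18 scan or a clinically indicated scan can catch it too. The other is that a gain of 5 to 9 points is the full range; that leaves out the lower cases in the table.

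**Re-dating rules belong in the SAP.** Agreed: the lack of one in the protocol is not a fault. What the protocol does fix is which scans are collected.

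**Conclusion.** The point holds. As written, the protocol schedules a tumor scan whose timing depends on the arm and which, for on-schedule Arm B completers, falls just before a 4-month landmark of about Day 122. With no true effect and a 25% rate in both arms, this gives lenvatinib about 5 to 6 points on PFS-4m and raises the one-sided error from 10% to about 22%. The range over scan timing is about 2 points and 12.5% to about 9 points and 34%. Partial uptake in Arm B, or some off-treatment scans in Arm A, gives about 3 to 4 points and 15 to 19%.

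These sizes rest on exponential progression, uniform visit timing, no deaths or censoring, and 4 months read as 121.75 days. The direction follows from the schedule and the dating rule for as long as the landmark precedes most Week 18 scans.

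**What to change.** In both copies of Table 5 and its tumor-assessment footnote, state that scans in both arms follow calendar weeks from Cycle 1 Day 1 whatever the treatment status, with clinically indicated scans in addition. For subjects without progression, drop the separate off-treatment scan and let the next calendar scan serve; for Arm B completers this is Week 18.

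For scans already taken, add a sensitivity analysis that moves progression first seen at an off-treatment scan to the next scheduled assessment, applied identically in both arms.

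Moving the landmark to cover the Week 18 window would also remove the PFS-4m bias, but it would leave the asymmetry in PFS dates, so it does not replace the schedule change.

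The cost is an edit to the table row and footnote plus one sensitivity analysis, and it saves a scan for Arm B completers whose off-treatment scan is additional. The drawback is that Arm B has no imaging exactly at the end of chemotherapy, although a calendar scan follows within weeks.
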